## 4. STUDY DESIGN

### 4.1. Study Design Overview

This study is a multicenter, randomized, double-blind, placebo-controlled trial designed to evaluate efficacy and safety of NTZ 600 mg administered orally twice daily for five days compared to a placebo for the treatment of mild or moderate COVID-19.

Subjects will be stratified according to the following criteria:

Severity of COVID-19 Illness:

- Mild illness defined as baseline assessments of (1) at least one respiratory domain\* with a baseline score  $\geq 2$  and (2) resting pulse  $< 90$  beats per minute and (3) resting respiratory rate  $< 20$  breaths per minute.
- Moderate illness defined as baseline assessments of (1) at least one respiratory domain\* with a baseline score  $\geq 2$  and either (2) resting pulse  $\geq 90$  beats per minute or (3) resting respiratory rate  $\geq 20$  breaths per minute.

\* For this purpose, respiratory domains shall include the following 5 FLU-PRO domains/subdomains: chest, cough, nose, throat and head.

Time from onset of symptoms to randomization:

<36 hours/ $\geq 36$  hours

Risk of severe illness (per CDC):

- At Increased Risk: Subjects with COPD, Type 2 diabetes mellitus, obesity (BMI  $\geq 30$ ), chronic kidney disease, sickle cell disease, serious heart conditions (such as heart failure, coronary artery disease, or cardiomyopathies), asthma (moderate or severe), cerebrovascular disease, cystic fibrosis, hypertension or high blood pressure, immunocompromised state (due to immune deficiencies, HIV, use of corticosteroids, or use of other immune-weakening medications), neurologic conditions (e.g., dementia), liver disease, pulmonary fibrosis, past or present history of smoking, thalassemia, or type 1 diabetes mellitus. Subjects who are  $\geq 65$  years of age.
- Not At Increased Risk: Subjects with none of the above conditions

Within strata, subjects will be randomized 1:1 to one of the following groups:

- Group 1 (NTZ): Two NTZ 300 mg tablets b.i.d. for 5 days

- Group 2 (Placebo): Two placebo tablets b.i.d. for 5 days

The study is expected to take place from July 2020 through January 2021.

We expect that a large number of subjects enrolled will be positive for Enterovirus/Rhinovirus (EV/RV). Efficacy and safety data for subjects who are positive for EV/RV at Baseline will be analyzed as part of concurrently enrolling study RM08-3009.

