## **8.4. Adverse Events and Serious Adverse Events**

### **8.4.1. Definitions**

The following definitions will apply to the reporting of adverse events:

1. **Adverse Event:** Any unwanted physical, psychological or behavioral change experienced by a subject during the course of the study and after taking the first dose of study medication regardless of its severity or relation to the study. Adverse events may include symptoms, signs, unexpected worsening of pre-existing conditions, clinically significant changes in laboratory values, diseases and syndromes, and significant and unexpected failures of pharmacological action of other medications. Symptoms of viral respiratory infections (VRIs) (cough, sore, throat, nasal obstruction, fatigue, headache, myalgia, or feverishness) will not be reported as adverse events.
2. **Serious Adverse Event:** Any adverse experience occurring at any dose that is fatal or life threatening; requires in-patient hospitalization or prolongation of an existing hospitalization; is a persistent significant disability/incapacity; is a congenital anomaly or birth defect; or is an important medical event that may not result in death, be life-threatening, or require hospitalization but, based upon appropriate medical judgment, may jeopardize the subject and may require medical or surgical intervention to prevent one of the outcomes listed above.
3. **Unexpected Adverse Event:** Any adverse experience that is not identified in nature, severity, or frequency in the Investigator's Brochure for NTZ.
4. **Severity of adverse events** will be assessed as mild, moderate, severe or potentially life-threatening by the Investigator using the Toxicity Grading Scale Tables provided in [Appendix 4](#) (derived and adapted from "Guidance for Industry: Toxicity Grading Scale for Healthy Adult and Adolescent Volunteers Enrolled in Preventive Vaccine Clinical Trials", US Dept. of HHS, FDA, CDER, September 2007 and the National Institutes of Health, National Cancer Institute Common Terminology Criteria for Adverse Events (CTCAE) version 5.0).
5. **Causality (relationship to treatment)** will be assessed as follows:

- *Definitely Related*: The adverse event is clearly related to the investigational agent(s) or research intervention: the adverse event has a temporal relationship to the administration of the investigational agent(s) or research intervention, follows a known pattern of response, and no alternative cause is present.

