2.3 Missing Data Conventions

Date variables with missing items will be imputed as shown in Table 2 below.

Table 2. Imputation Rules for Missing Dates

Data	Handling Convention
Adverse event onset date	If onset date is completely missing, impute with the date of first dose. If year is missing, impute with the year of enrollment.

Data	Handling Convention
	
If only year or if year and day are present:
 
 • If year = year of first dose, then set month and day to the date of the first dose. • If year < year of first dose, then set month and day to December 31. • If year > year of first dose, then set month and day to January 1. 
If month and year are present, but day is missing:
 
 • If year = year of first dose and 
 ◦ If month = month of first dose, then set day to day of first dose. ◦ If month < month of first dose, then set day to the last day of the month. ◦ If month > month of first dose, then set day to the first day of the month. • If year < year of first dose, then set day to the last day of the month. • If year > year of first dose, then set day to the first day of the month. • For all other cases, set onset date to the date of first dose.
Adverse event end date	If the end date is partially or completely missing and AE outcome is not one of the following: RECOVERING/RESOLVING, NOT RECOVERED/NOT RESOLVED, UNKNOWN, or missing, then set to the last date the subject was known to be in the study. Otherwise, if AE outcome is one of the following: RECOVERING/RESOLVING, NOT RECOVERED/NOT RESOLVED, UNKNOWN, or missing, then set the end date to missing.
Concomitant medications start date	
If start date is completely missing, it will not be imputed.
 
If only year or if year and day are present, set the month and day to January 1.
 
If year and month are present and day is missing, set day to the first day of the month.

Concomitant medications end date	
If end date is missing, frequency is “1X” and the medication is not listed as “ONGOING”, then end date should be set to equal the start date.
 
If end date is completely missing, it will not be imputed.
 
If only year or if year and day are present, set the month and day to December 31.
 
If year and month are present and day is missing, set day to the last day of the month.

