5.2 Description of Safety Analyses

Adverse Events

Adverse events will be graded by the investigator according to the “Guidance for Industry: Toxicity Grading Scale for Healthy Adult and Adolescent Volunteers Enrolled in Preventive Vaccine Trials” ([FDA/CDER, 2007](#)) as adapted in the Study Protocol. The investigator will also assess causality (relationship to treatment) as *Definitely related*, *Probably related*, *Possibly related*, and *Unrelated*. AEs will be coded using the Medical Dictionary for Regulatory Activities version 23.0 or higher (MedDRA®).

Treatment-emergent AEs (TEAEs), defined as any AE that occurs after a subject receives the first dose of the assigned study treatment, will be summarized by the number and proportion of subjects reporting at least one occurrence of the AE. Frequencies and rates of each TEAE will be summarized by MedDRA system organ class (SOC) and by preferred term within SOC, by severity grade, and relation to treatment for each treatment group. The rate calculation will be based on the number of subjects in the ITT population for the relevant treatment group.

Treatment emergent serious adverse events (TESAEs) will be summarized and displayed by frequency and rate by MedDRA SOC and by preferred term within SOC.

A by-subject AE data listing of all adverse events including verbatim term, coded term, grade, and relation to treatment will be provided.

Laboratory Tests

Clinical laboratory tests will be performed at baseline and on Day 10. The following clinical laboratory tests will be performed:

Hematology:

Hemoglobin, hematocrit, complete white blood count (total and differential), platelet count, random blood glucose, total cholesterol, HDL, LDL, and triglycerides.

Clinical Chemistry:

Albumin, AST, ALT, GGT, alkaline phosphatase, bilirubin (total and direct), BUN, creatinine, sodium, potassium, and chloride.

Urinalysis:

Appearance, glucose, protein, and blood.

Clinical laboratory results and the change from baseline (CFB, baseline defined as the value at the baseline visit) will be summarized for the ITT population with summary

statistics (mean, standard deviation, n, minimum, median, maximum) by visit for each treatment group.

Clinical laboratory results will be classified according to the toxicity grading tables in the protocol Appendix 4 and will be summarized using a shift table from baseline according to these categories.

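### SAP Table 2 gives an adverse event with no recorded year the enrolment year, so a January 2021 onset in a December 2020 enrollee is dated to January 2020, before first dose

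*SAP*

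**What the plan says.** SAP section 2.3, Table 2, sets these rules for an incomplete adverse-event onset date:

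- Whole date missing: "If onset date is completely missing, impute with the date of first dose".
- Year missing: "If year is missing, impute with the year of enrollment".
- Month missing: "If year = year of first dose, then set month and day to the date of the first dose".
- Month and year present, day missing, same year as first dose: among other rules, "If month < month of first dose, then set day to the last day of the month".
- At the end of that last branch: "For all other cases, set onset date to the date of first dose".

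SAP section 5.2 takes a treatment-emergent adverse event to be one "defined as any AE that occurs after a subject receives the first dose of the assigned study treatment". Protocol section 8.4.1 already limits adverse events to those arising "after taking the first dose of study medication regardless of its severity or relation to the study". On timing, Protocol section 4.1 says: "The study is expected to take place from July 2020 through January 2021". The protocol synopsis has adverse events assessed from baseline through Day 28, and the Schedule of Assessments gives that contact a window of 3 days either side.

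**The concern.** Using the enrolment year is harmless in a trial that stays within one calendar year. This one does not. The protocol's revision history moves the expected end of enrolment from December 2020 to January 2021, so December enrolment was foreseen, and those subjects are followed into January. For them the enrolment year is the wrong year for any January event, and the rule puts the onset about eleven months before dosing.

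The rule is also out of line with its neighbours in Table 2. When less is known (no month, or no date at all), the onset goes to first dose. When more is known (the month, or the month and day), it can go to the previous January.

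What is at stake is the safety summary. Every adverse-event summary table in SAP section 8.0 (14.3.1.1 to 14.3.1.5, including the serious-event table) is restricted to treatment-emergent events. No table is planned for other events.

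**Working it through.** The plan gives no figure to reproduce here, so the check applies the rules to dates.

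**Inputs.** The onset rules are those of SAP Table 2. Enrolment and first dose fall on the same day, Day 1 (SAP section 1.2). Follow-up runs to Day 28, or Day 31 with the +3-day window (Protocol synopsis and Schedule of Assessments). First-dose dates from 14 July 2020 to 31 January 2021 are an assumption, taken from the date of protocol version 1.0 and the stated study period. The rules are read in sequence: the missing year is filled first, and the day rule is then applied.

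**Which subjects can be affected.** Day 28 is first dose plus 27 days; Day 31 is first dose plus 30 days.

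| First dose | Day 28 | Day 31 |
|---|---|---|
| 1 Dec 2020 | 28 Dec 2020 | 31 Dec 2020 |
| 2 Dec 2020 | 29 Dec 2020 | 1 Jan 2021 |
| 4 Dec 2020 | 31 Dec 2020 | 3 Jan 2021 |
| 5 Dec 2020 | 1 Jan 2021 | 4 Jan 2021 |

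January follow-up therefore begins with first dose on 5 December at the nominal visit day, or 2 December with the window. It applies to all later December enrollees.

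**Worked case.** First dose 20 December 2020, true onset 8 January 2021, year not recorded. In 2020, a leap year, 20 December is day 355.

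| Known parts | Imputed onset | Days before first dose |
|---|---|---|
| Month and day | 8 Jan 2020 | 355 − 8 = 347 |
| Month only | 31 Jan 2020 | 355 − 31 = 324 |
| Day only | 20 Dec 2020 | 0 |
| Nothing | 20 Dec 2020 | 0 |

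In the second row the year becomes 2020, January precedes December, and the last-day-of-month rule applies.

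**All combinations.** There are 202 first-dose dates and 31 onset days, so 202 × 31 = 6,262 combinations. Those that cross the year end have first dose from 2 to 31 December, giving 1 + 2 + … + 30 = 465. With the month known, all 465 are imputed before first dose, whether or not the day is known. No other enrolment month gives a pre-dose date. With the month unknown, none does. These are counts of possible date pairs, not expected frequencies.

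**The catch-all does not help.** The line sending remaining cases to first dose sits under the branch for a missing day. A record with month and day known does not enter that branch. A month-only record has already matched an earlier line in it.

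**The case against.** The strongest reply is that no event need be lost. Both the protocol's definition of an adverse event and the SAP's definition of treatment-emergent refer to when the event occurred, not to an imputed date. On those definitions, every event properly recorded as an adverse event is treatment-emergent. A reader might infer that the rule in itself removes events from the treatment-emergent tables. The documents do not support that, because the SAP never says the flag is derived from the imputed date. This part of the reply stands, and the consequence has to be stated as conditional. It does not clear the rule: the SAP describes no other use for an imputed onset date, and a date before first dose contradicts the protocol's definition however the flag is set.

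A reader might also infer that every record with a missing year is affected. Table 2 shows otherwise: without a month, the onset goes to first dose.

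The second reply is rarity, and it also stands. Data go into an electronic system with monitor verification and queries (Protocol section 10.1.5.1). Subjects are contacted daily on Days 2 to 7, seen on Days 4, 10 and 22, and contacted on Day 28. A record with a month but no year should draw a query. Serious events reach the sponsor within 24 hours (Protocol section 8.4.3), and all adverse events stay in the listings (SAP section 5.2). Nothing disappears from the report altogether. These safeguards reduce the number of such records but do not correct the rule for any that remain.

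**Conclusion.** The rule is wrong as written for one defined group: first dose from 5 December (2 December with the window) to 31 December 2020, true onset in January 2021, month known and year missing. For these records the imputed onset always precedes first dose. Loss from the summary tables follows only if the treatment-emergent flag uses the imputed date. In that case the error runs one way, towards too few treatment-emergent events.

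The documents give no rate of missing years. With electronic capture and about 28 days of follow-up, few records are expected. No efficacy analysis is touched. This is a minor defect, worth correcting because correction is cheap. The conclusion rests on reading the Table 2 rules in sequence and on enrolment proceeding through December as planned.

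**What to change.** Replace the missing-year line in SAP Table 2 with: *If year is missing and month is known, impute the first year that does not place the known month before the month of first dose; query any resulting date outside the subject's study participation.* In the worked case this gives 8 January 2021 (month and day known) or 1 January 2021 (month only). Across the 465 cross-year combinations, pre-dose imputations fall to 0.

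The comparison should be by month. A rule taking the earliest date on or after first dose would turn an onset recorded as 10 December, with first dose on 20 December 2020, into 10 December 2021, after the study has ended. The month comparison gives 10 December 2020, which is before first dose and so goes to query.

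Add one sentence on the flag: *An event recorded as an adverse event is counted as treatment-emergent unless its recorded, non-imputed date parts show onset before first dose.* A blanket ban on pre-dose imputed dates would conflict with the Table 2 branches for a recorded year or month before first dose. This sentence leaves the branches for recorded years intact.

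The cost is a small SAP edit and an occasional data query.

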2.4 Interim Analyses

No interim analyses are planned.

2.4.1 Analysis Timing Considerations

It is anticipated that central lab data for the serology, quantitative SARS-CoV-2 RNA measured by RT-PCR, and the pharmacokinetics (PK) analysis of blood samples may be delayed at the end of the study, due to sample processing timelines. These lab data will be transferred outside of the clinical database and will not impact the timing of database lock. Further, these data have no impact on the primary and secondary efficacy

objectives of the study.

At the Sponsor's discretion, the final unblinded tables, listings, and figures (TLFs) using the locked database may be generated and shared with the Sponsor prior to completion of the serology, RT-PCR, and PK sample testing. The central lab responsible for processing the serology, RT-PCR, and PK data will have no knowledge of the subjects' treatment information nor any knowledge of the study outcomes while samples are being processed. At the completion of sample processing, the central lab will transfer the serology, RT-PCR, and PK data directly to SCS to incorporate into the final study datasets. The SAS programs used to generate the final study datasets will be re-run to include these new data files, and the final set of all TLFs will be generated. This re-run of final TLFs will be conducted for the sole purpose of including the new central lab data; the TLFs generated prior to completion of serology, RT-PCR, and PK sample testing will remain unchanged.

2.5 Study Center Considerations in the Data Analysis

A study center is defined as a treatment administration site or group of treatment administration sites under the control and supervision of the same Principal Investigator (PI). There will be no selective pooling of study centers – all sites will be pooled. The study is planned to be conducted at multiple sites.

2.6 Documentation and Other Considerations

The data analyses will be conducted using SAS® Software, version 9.4 or later.

3.0 Analysis of Baseline Subject Characteristics

Baseline and demographic characteristics of the ITT and ITTI populations will be summarized. Continuous variables (age, baseline height, baseline weight) will be summarized via mean, standard deviation, minimum, median, maximum, interquartile range, and number of non-missing responses. Categorical variables (gender, race, and ethnicity) will be summarized via counts and percentages.

A detailed listing of baseline data for each subject in the ITT population will also be provided.

4.0 Analysis of Efficacy

4.1 Efficacy Variables

4.1.1 Primary Efficacy Variable

The primary efficacy variable is the Time to Sustained Response. This is defined as the time in days from the first dose of study medication to the time of the first diary entry meeting all the criteria for a sustained response (i.e., Time of Sustained Response).

Sustained response to treatment is defined as a decrease in the total FLU-PRO score from the previous, subject assessment that symptoms are at least “somewhat better than yesterday”, no oral temperature ≥ 100.4 F in the preceding 24 hours, and no future increase in any of the FLU-PRO domains except within the following levels:

FLU-PRO Domain	Background Level
Body/Systemic	0.56
Throat	0.67
Eyes	0.67
Gastrointestinal	2.00
Head	2.00
Nose	Larger of score at time of response or 0.75
Chest	Score at time of response
Cough	Larger of score at time of response or 1.75

Subjects must have at least one diary following the time of sustained response in which there is no relapse, meaning that a subject cannot achieve sustained response at the last diary entry.

Situation	Censoring rule
Has Time of Sustained Response	Not censored.
Hospitalized due to COVID-19	Censored at Day 21 (i.e., hour 504).
Died (any cause)	Censored at Day 21 (i.e., hour 504).
No Time of Sustained Response	Censored at time of last diary entry without sustained response.

4.1.2 Key Secondary and Exploratory Efficacy Variables

The key secondary efficacy variable is Progression to Severe COVID-19 Illness. Any subject meeting both of the following criteria has advanced to Severe COVID-19 Illness:

1. Shortness of breath at rest.
2. $\text{SpO}_2 \leq 93\%$ on room air, or $\text{PaO}_2/\text{FiO}_2 < 300$.

The exploratory efficacy variables are:

1. Proportion of subjects positive for SARS-CoV-2 by Aptima® SARS-CoV-2 assay at Days 4 and 10.
2. Change from baseline of quantitative SARS-CoV-2 RNA measured by RT-PCR at Days 4 and 10.
3. Hospitalization due to COVID-19 or complications thereof.
4. Mortality due to COVID-19 or complications thereof.

4.2 Efficacy Analysis

4.2.1 Primary Efficacy Analysis

The Time to Sustained Response will be summarized with descriptive statistics (n, mean, standard deviation, minimum, maximum, median, and interquartile range) with censored values excluded from the descriptive statistics.

The Time to Sustained Response will be tested for differences between the treatment groups using a stratified Gehan-Wilcoxon test at $\alpha = 0.05$ using the stratification at randomization. Kaplan-Meier curves will be provided. The hypotheses being tested are

$$H_0: \text{The survival curves of the NTZ Group and the Placebo Group are identical.}$$
$$H_1: \text{The survival curves of the NTZ Group and the Placebo Group are different.}$$

The analysis table will include the Kaplan-Meier estimates of the mean and median for each treatment group.

Subgroup analyses will be conducted on the subgroups specified in Section 2.2.2. Descriptive statistics and Kaplan-Meier estimates of the mean and median Time to Sustained Response will be provided by subgroup, but there will be no hypotheses tested in these subgroups.

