#### **4.2.4.1. Choice of Signs and Symptoms Required for Inclusion**

Data from studies RM08-3004 and RM08-3005 indicate that, in subjects infected with influenza, *EV/RV* or seasonal coronavirus, subjects with low symptom scores for the head, throat, nose, chest and cough symptom domains in the absence of elevated pulse or respiratory rate, illness may be expected to resolve quickly. These subjects have less opportunity to benefit from antiviral treatment. Further, subjects who indicate that symptoms are already improving are also unlikely to benefit from treatment. Therefore, subjects will be required to have a score of  $\geq 2$  for two respiratory symptom domains (head, throat, nose, chest, or cough) or a score of  $\geq 2$  for one respiratory symptom domain in the presence of elevated vital signs (pulse  $\geq 90$  beats per minute or respiratory rate  $\geq 16$  breaths per minute). Subjects will be excluded if they report having no symptoms (global assessment), being at their usual health, that their symptoms do not interfere with their usual activities, or that their symptoms have improved since yesterday. Subjects presenting with signs or symptoms consistent with severe COVID-19 (resting shortness of breath, resting pulse  $\geq 125$ , resting respiratory rate  $\geq 30$ ) will also be excluded from the study.

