### **8.1.5. Screening FLU-PRO**

The FLU-PRO questionnaire will be administered during the Screening visit to confirm symptoms required for eligibility.

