#### 9.4.1. Efficacy Analyses

Efficacy analyses will be based on a population consisting of all subjects randomized who receive at least one dose of study medication and are positive for SARS-CoV-2 by Aptima® SARS-CoV-2 Assay at Baseline. For time-to-event analyses, a test of significance (as described in the following) will be performed with descriptive statistics provided, including the use of Kaplan-Meier figures.

There will be one primary efficacy analysis:

- Time to Sustained Response for the NTZ treatment group will be compared to that of the placebo treatment group using a stratified Gehan-Wilcoxon test ( $\alpha=0.05$ ) where stratification will follow that used for randomization. Subjects without a Sustained Response recorded will be treated as censored as of the last diary without a documented Sustained Response, except for subjects who are hospitalized or die during the study, who will be censored at Day 21 (hour 504).

Sensitivity analyses for the primary efficacy analysis will be described in the Statistical Analysis Plan.

If the primary analysis is significant at the 0.05 level, the key secondary efficacy analysis will be formally evaluated at the 0.05 level as follows:

- Proportions of subjects progressing to Severe COVID-19 Illness will be compared between the treatment groups using a Cochran-Mantel-Haenszel (CMH) test stratified by the randomization strata.

Exploratory analyses will be performed as follows:

- Proportions of subjects positive for SARS-CoV-2 by Aptima® SARS-CoV-2 Assay at study Day 4 and Day 10 will be compared between the treatment groups using a Cochran-Mantel-Haenszel (CMH) test stratified by the randomization strata.
- Mean changes from baseline in quantitative SARS-CoV-2 RNA measured by RT-PCR at Day 4 and Day 10 will be compared using a t-test.
- Proportions of subjects hospitalized due to COVID-19 or complications thereof will be compared across the treatment groups using a CMH test stratified by the randomization strata.
- Proportions of subjects with mortality related to COVID-19 or complications thereof will be compared across the treatment groups using a CMH test stratified by the randomization strata.

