2.2.2 Stratum and Subgroup Definitions

Subjects will be stratified on the basis of Severity of COVID-19 illness (Mild or Moderate), Time from onset of symptoms to randomization (less than 36 hours or at least 36 hours), and Risk of severe illness per CDC guidelines (At increased risk or not at increased risk). There will be a total of 8 strata.

The primary efficacy variable of the Time to Sustained Response will also be summarized by the following subgroups:

- Risk of severe COVID-19 illness per CDC guidelines (At increased risk or not at increased risk)
- Age (12-17, 18-64, ≥ 65)
- Sex
- Race (White/Non-white)

Safety analyses will be grouped by treatment received.

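### The primary test and its sensitivity analyses leave out the Screening FLU-PRO score; a pre-specified adjustment costs almost nothing and may add power, but the gain is unknown and could be zero

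*SAP*

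**What the plan says.** The primary analysis in SAP 4.2.1 reads: "The Time to Sustained Response will be tested for differences between the treatment groups using a stratified Gehan-Wilcoxon test". Protocol 9.4.1 names the same test as the single primary efficacy analysis, "where stratification will follow that used for randomization". The factors are illness severity, time from symptom onset (split at 36 hours) and CDC risk group. SAP 2.2.2 adds: "There will be a total of 8 strata".

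The severity factor is defined in Protocol 4.1. One category is "Mild illness defined as baseline assessments of (1) at least one respiratory domain" scoring 2 or more, with pulse below 90 and respiratory rate below 20. The other is "Moderate illness defined as baseline assessments of (1) at least one respiratory domain" scoring 2 or more, with pulse of at least 90 or respiratory rate of at least 20.

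On collection, Protocol 8.1.5 says: "The FLU-PRO questionnaire will be administered during the Screening visit". Under Protocol 8.1.6, randomisation follows only once all screening procedures are complete.

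The sensitivity analyses in SAP 4.2.1.1 to 4.2.1.3 are a log-rank test, a per-protocol analysis and a missing-data analysis. The subgroups in SAP 2.2.2 are risk, age, sex and race. The baseline summary in SAP 3.0 lists age, height, weight, gender, race and ethnicity. None of these uses a FLU-PRO score.

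**The concern.** A symptom score measured before randomisation is an obvious candidate covariate when the endpoint is built on the same instrument. The severity factor does not stand in for it. A subject with all five respiratory domains at 2 or more and normal vital signs is classed as mild. So is a subject with a single domain at 2, pulse below 90 and a respiratory rate of 16 to 19, who qualifies through inclusion criterion 3c.

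If the score predicts time to Sustained Response, the planned rank test leaves that variation in its error term. A chance difference in symptom burden between the arms would be neither adjusted for nor shown in a baseline table. There is one primary test, and the key secondary endpoint is formally tested only if the primary succeeds, so any lost power affects both.

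**Working it through.** **1. The plan's own figures.** The 288 and 312 subjects for 90% power cannot be reproduced, because the Kaplan-Meier curves used as input are in a figure that is not shown. Two things can be checked.

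- Allowance for about 10% loss: 312/(1 − 0.10) = 346.7, so 347; or 312 × 1.10 = 343.2, so 344. Both fit the planned 350.
- Implied effect, by Schoenfeld's formula with 1:1 allocation and two-sided alpha 0.05: (ln HR)² = 4(1.960 + 1.282)²/events = 42.0/events. With 312 subjects, of whom 100% to 70% respond, events run from 312 to 218 and the hazard ratio for response from 1.44 to 1.55.

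**2. What the documents say about prognosis.** Protocol 4.2.4.1 describes "subjects with low symptom scores for the head, throat, nose, chest and cough symptom domains in the absence of elevated pulse or respiratory rate" and says that in them "illness may be expected to resolve quickly". The viruses are influenza, EV/RV and seasonal coronavirus. The statement is the reason for inclusion criterion 3, which largely keeps such subjects out. It therefore supports prognostic relevance within the trial only indirectly. On the other side, criterion 3 sets a floor on respiratory domains and no ceiling. It leaves the body/systemic, eye and gastrointestinal domains unrestricted. No hazard ratio per unit of score is given, so a range has to be assumed.

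**3. Simulation.** From the documents: N = 312, 1:1 allocation, 8 strata, daily diaries, censoring at day 21, and a placebo median of 201.8/24 = 8.4 days (the 52 coronavirus-infected subjects in Protocol 2.2.4), used only to set the time scale. Assumed: exponential times, equal-sized non-prognostic strata, no dropout, and a log-hazard linear in the score. In each scenario the treatment effect was set so that the planned test has about 90% power. There were 3,000 replicates, so the Monte Carlo standard error near 90% is √(0.9 × 0.1/3000) = 0.5 points.

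The adjusted test gives each subject a Gehan score within the stratum: the number known to respond later minus the number known to respond earlier. It regresses these scores on treatment and baseline score, both centred within stratum, and tests the treatment coefficient. The comparator adds score tertiles to the strata: 8 × 3 = 24 strata, averaging 312/24 = 13 subjects.

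| Assumed HR per SD of score | Planned test | Adjusted for continuous score | 24 strata |
|---|---|---|---|
| 1.00 | 90.9% | 90.8% (−0.1) | 86.7% (−4.2) |
| 1.22 | 90.3% | 91.2% (+0.9) | 87.0% (−3.3) |
| 1.49 | 90.6% | 93.1% (+2.5) | 90.1% (−0.5) |
| 2.01 | 90.5% | 96.0% (+5.5) | 93.8% (+3.3) |

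With no treatment effect, all three tests rejected in 4.1% to 4.9% of replicates in every scenario.

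**4. Chance imbalance.** At N = 350 the standard error of the between-arm difference in a standardised score is 2/√350 = 0.107 SD. About 1 trial in 20 therefore has an imbalance of at least 1.96 × 0.107 = 0.21 SD in one direction or the other. At an assumed hazard ratio of 1.49 per SD, that moves the log hazard ratio by 0.21 × ln 1.49 = 0.08. Against the implied design effect (ln 1.44 = 0.36 to ln 1.55 = 0.44) this is about a fifth. If the score is not prognostic, the shift is zero.

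**The case against.** The strongest case is that the plan is sound as written. A Gehan test stratified by the randomisation factors is conventional and valid, and the sample size was computed for it. With 350 enrolled and 10% lost, 315 remain, against 312 needed. This stands: nothing here is an error.

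A reader might infer from Protocol 4.2.4.1 that low scores are known to predict fast recovery in this trial, so that power is certainly being lost. The documents do not support that. The statement joins low scores with normal vital signs, which the severity factor partly carries. It concerns other viruses and five respiratory domains, not the total score, and it serves to exclude the subjects it describes. This part of the objection stands in full.

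The endpoint also differs from symptom resolution. Sustained Response requires improvement on the previous diary and no later worsening beyond set levels, and for nose, chest and cough those levels can rise with the score at response. A high scorer may therefore respond while still symptomatic, and the direction of any association is uncertain. This limits what can be said about size. It does not defeat the adjustment, whose gain depends on the strength of the association and not on its sign.

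A reader might also take chance imbalance to mean that the planned test is biased. It is not: the type I error of a randomisation-valid test already allows for such imbalance.

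**Conclusion.** The point holds as a free improvement whose gain is unknown. The omission is plain in both documents, the severity factor does not grade symptoms, and the score is already collected before randomisation. Adjusting for the continuous score would add about 0 points of power if it is not prognostic among enrolled subjects, and about 1, 2.5 or 5.5 points at assumed hazard ratios per SD of 1.22, 1.49 or 2.01.

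These figures rest on the simulation assumptions above. If the eight strata already carry some of the same information, the gain is smaller. They also cover one covariate, so no gain from continuous hours since onset has been shown.

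It would be too strong to say that any use of the score is free. Extra strata cost about 3 to 4 points when the association is weak or absent. Confidence is high on the omission and moderate on the size.

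**What to change.** Before unblinding, pre-specify a stratified Gehan analysis adjusted for the continuous Screening FLU-PRO total score, as a randomisation-based nonparametric ANCOVA on within-stratum Gehan scores. The simulation used the least-squares counterpart of this method. Name the Screening score explicitly, because the first home diary on Day 1 is completed after the first dose.

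There are two ways to place it:

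- As the primary test, with the unadjusted stratified test reported beside it. This means amending Protocol 9.4.1 as well as SAP 4.2.1.
- At minimum, as the first sensitivity analysis. Protocol 9.4.1 leaves sensitivity analyses to the SAP, so SAP wording and one added table are enough.

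In either case, add the baseline score by arm to the summaries in SAP 3.0. Do not add score categories to the existing 8 strata. Continuous hours since onset may be included as a second covariate, without claiming a gain.

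The sponsor could estimate the association beforehand from the 1,467 infected subjects in RM08-3004 and RM08-3005 (Protocol 4.2.7), restricted to those who would meet inclusion criterion 3. The cost is wording and a short program; no new data are needed.
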